8.2.2 MISSING/PARTIAL DATES FOR CONCOMITANT MEDICATIONS

Missing/Partial start dates for concomitant medications will be imputed as follows. The original dates will be displayed in data listings and the imputed dates will be used in derivations only for the differentiation of prior and/or concomitant medications.

- Dates with missing day only will be imputed as the 1st of the month unless the month and year are the same as the month and year of the first exposure to treatment, in which case the missing day will be imputed as the first exposure to treatment day.
- Dates with both day and month missing will be imputed as 1 Jan unless the year is same as the year of first exposure to treatment, in which case missing day and month will be imputed as the first exposure to treatment day and month.
- A completely missing date will be imputed as the first exposure to treatment unless the concomitant medication end date is on or before the first dose date of study medication, in which case the missing date will be imputed as 1 Jan of the same year as the end date.

Missing/Partial end dates for concomitant medications will be imputed as follows:

- Dates with missing day only will be imputed as the last day of the month unless the month and year are the same as month and year of the last exposure to treatment, in which case missing day will be imputed as the last exposure to treatment day.
- Dates with both day and month missing will be imputed as 31 Dec unless the the year is the same as the year of the last exposure to treatment, in which case missing day and month will be imputed as the last exposure to treatment day and month.

- Complete missing dates will not be imputed.

8.2.3 MISSING DATA IN EFFICACY ANALYSIS

Missing data in efficacy analysis will be handled as follows:

- Using last observation carried forward (LOCF)
- Imputing missing as failure
- Using observed data only

Details are specified in [Section 13.1](#).

8.3 Definition of Baseline

Baseline is defined as the last non-missing measurement on or before the study treatment date. If the Baseline visit (i.e. Visit 2) is missing, use the non-missing measurement from Screening visit (i.e. Visit 1) unless there is an unscheduled visit after Screening visit and before Baseline visit. Measurements from unscheduled visit on the study treatment date can not be used as baseline without the knowledge of if the measurement is taken before or after treatment exposure.

8.4 Data Analysis Conventions

All data analyses will be performed by SDC. Statistical programming and analyses will be performed using SAS® Version 9.4 or higher. Output will be provided in rich text format (RTF) for tables and portable document format (PDF) for tables, listings, and figures using landscape orientation. All study data will be listed by treatment (and phase [initial vs randomized] for CF1), subject and visit (as applicable).

Summaries for continuous and ordinal variables will include the number of observations (n), arithmetic mean, standard deviation (SD), median, minimum, and maximum. Minima and maxima will be reported with the same precision as the raw values; means and medians will be presented to one additional decimal place than reported in the raw values. Standard deviations will be presented to two additional decimal places than reported in the raw values. Summaries for discrete variables will include number and percentages. All percentages will be rounded to one decimal place (i.e., XX.X%). Change from baseline will be calculated as follow-up visit minus baseline.

All statistical tests will be two-sided with a significance level of 0.05 ($\alpha = 0.05$) unless otherwise specified. Confidence intervals for differences between treatment groups will be two-sided at 90% and 95% confidence. All p-values will be rounded to four decimal places; p-values less than 0.0001 will be presented as "<0.0001"; p-values greater than 0.9999 will be presented as ">0.9999."

Unless otherwise specified, summaries will be presented by treatment group and, where appropriate, visit.

8.5 Adjustments for Multiplicity

No adjustments for multiplicity are planned.

9. Disposition of Subjects

The following disposition items will be summarized:

- The number of subjects who were screened, screen failed, and treated
- The number and percentage of subjects in each analysis population
- The number and percentage of subjects who completed the study
- The number and percentage of subjects who discontinued from the study and the reasons for premature discontinuation. COVID-19 related discontinuation will be identified.
- The number and percentage of subjects with any deviations, any major or minor deviations, any deviations related to COVID-19. Major or minor deviations will be assigned by the Sponsor. COVID-19 related deviations can be major or minor as assigned by the Sponsor.

All percentages will use the number of subjects treated as the denominator, overall and by treatment group, unless indicated otherwise.

In addition, subject disposition (for safety population and for screen failed subjects), protocol deviations, inclusion/exclusion criteria violations listings will be provided. A separate data listing for COVID-19 related protocol deviations will be provided.

10. Demographic and Pretreatment Variables

10.1 Demographic Variables

The demographic variables collected in this study include age, gender, race, and ethnicity. Subjects who record more than one race will be grouped into a single category denoted as multi-racial. Demographic variables will be summarized and listed.

Age (years) will be summarized, overall and by treatment, using continuous descriptive statistics. Age will also be categorized as follows: <65 years and ≥65 years. Age will be reported in years and calculated using the following formula:

$$\text{Age} = (\text{Informed Consent Date} - \text{Date of Birth}) / 365.25, \text{ truncated as an integer}$$

The number and percentage of subjects will be presented, overall and by treatment, for age category, gender, race, and ethnicity.

Subject listings will be provided for demographic variables and childbearing potential for female subjects.

11. Medical History and Concomitant Medications

11.1 Medical History

A medical history will be obtained at the Screening visit. Medical history will be coded using Medical Dictionary for Regulatory Activities (MedDRA) Version 21.1.

Medical history will be summarized using discrete summary statistics and presented by treatment group at the subject level by System Organ Class (SOC) and Preferred Term (PT) using the Safety population. Ocular and non-ocular medical history will be summarized separately. If a subject reports the same PT multiple times within the same SOC, that PT will only be reported once within that SOC. As with the PT, if a subject reports multiple conditions within the same SOC, that SOC will only be reported once.

Listings of medical history will be generated separately for ocular and non-ocular data.

11.2 Prior and Concomitant Medications

Prior and concomitant medications will be coded using World Health Organization (WHO) Drug Dictionary (WHODrug Global B3, September 2018) and summarized to the therapeutic drug class (Anatomical Therapeutic Chemical [ATC] 4 classification) and preferred name. If the ATC 4 classification is not provided, the next lowest classification that is provided in the coding dictionary will be used. The preferred name will be defined as the active ingredient; if the active ingredient is not provided or includes more than two ingredients (e.g., multivitamins), then the drug name will be summarized as the preferred name.

Concomitant medications are defined as those medications listed as having been taken (1) prior to initiation of study medication administration and continuing for any period of time following the first administration of study medication or (2) at any time following the first administration of study medication.

Prior and concomitant medications will be summarized for all subjects. Medications will be tabulated for each treatment group using frequencies and percentages. Subjects may have more than 1 medication per ATC text. At each level of subject summarization, a subject will be counted once if he/she reports 1 or more medications. Percentages will be based on the number of subjects in each treatment group. Listings of prior and concomitant medications will be generated for ocular and non-ocular data.

12. Implant Residual Assessment

Duration of implant visibility in days will be calculated as: (End Date - Date of Implant Injection) + 1, where the end date is defined as the latest date at which the implant is visible or date of implant injection for subjects whose implants are not visible at any of the follow up visits. Vitreous implant visualization will also be summarized at each visit by treatment group using categorical statistics. A subject listing will be provided for vitreous implant residual assessment.

13. Efficacy Analyses

The efficacy analyses will include the following:

- Percentage of subjects with ≥ 15 -letter improvement compared to baseline BCVA (assessed by ETDRS) at Month 6.
- Change from baseline in CRT as assessed by SD-OCT at Months 1, 2, 3, 4, 5, and 6
- Change from baseline BCVA letter score at Months 1, 2, 3, 4, 5, and 6
- Percentage of subjects with a ≥ 10 -letter improvement compared to baseline BCVA at Months 1, 2, 3, 4, 5, and 6
- Percentage of subjects with a ≥ 10 -letter worsening compared to baseline BCVA at Months 1, 2, 3, 4, 5, and 6
- Percentage of subjects with a ≥ 15 letter improvement compared to baseline BCVA at Months 1, 2, 3, 4, 5 and 6
- Percentage of subjects with a ≥ 15 letter worsening compared to baseline BCVA at Months 1, 2, 3, 4, 5, and 6
- Percentage of subjects receiving rescue therapy overall

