Investigational Product, Dose, and Mode of Administration:

- AR-1105-CF1, 340 µg (target dose) administered intravitreally (2 implants, single injection)
- AR-1105-CF2, 340 µg (target dose) administered intravitreally (2 implants, single injection)

Study Duration:

Overall duration of the study is approximately up-to 18 months. This includes up to a 1-month screening period, followed by an enrollment period of up-to 6 months. Each subject in both Cohorts will complete a 6-month primary evaluation period. Residual implant assessment will be performed at Day 8 and at Months 1, 2, 3, 4, 5, and 6, and if necessary at monthly visits thereafter until they require retreatment, following the criteria provided for escape to rescue therapy, or until 1 month after the implant is no longer visible, or to Month 9, whichever comes first.

Safety Assessments (see Table 1):

Assessed by evaluating changes from baseline in the following (see statistical analysis plan [SAP] and Manual of Procedures [MoP] for details):

- Intraocular pressure (IOP) by Goldmann applanation tonometry
- BCVA by ETDRS method
- 3 field Fundus Photography (FP)
- Gonioscopy
- Slit-lamp biomicroscopy
- Dilated fundus examination
- Retinal thickness by SD-OCT (Cirrus (Zeiss), or Spectralis (Heidelberg) instrument)
- Fluorescein Angiography (FA)
- Vital signs (heart rate and blood pressure)
- Non- fasting clinical laboratory tests (clinical chemistry and hematology)

- Serum or urine pregnancy tests for females of childbearing potential
- Adverse Events

Efficacy Assessments (see Table 1):

Assessed by evaluating the following (see SAP and MoP for details):

- BCVA by ETDRS method
- Central Retinal/Foveal Thickness (CRT/CFT) as assessed by SD-OCT
- Fluorescein Angiography and Fundus exam
- Percentage of subjects requiring rescue therapy overall and by visit

Other secondary efficacy analyses may be carried out as described in the study SAP.

Statistical Methods:

[REDACTED]

Sample Size

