6.10.2 Non-Completing Subject

A non-completing subject is defined as one who exits the study by their own volition or at the discretion of the Investigator and/or the study Medical Monitor. Any subject may decide to voluntarily withdraw from the study at any time without prejudice. In this event, Investigator will make every attempt to complete all assessments scheduled for the final (Month 6) visit.

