7.4 Follow-up Visits ([REDACTED] ± 3 days as required for residual implant assessment)

Monthly safety visits should be scheduled if, following the assessments at Month 6 (Visit 9) are completed, it is noted that the vitreous still contains visible implant. At these visits, the subject will be queried regarding any changes to their ocular or medical health status since the previous visit, and also if there have been any changes to their ongoing medications or procedures. Vital signs (heart rate and blood pressure) will be collected.

The following procedures will be conducted OU:

- BCVA by ETDRS following manifest refraction
- Slit-lamp biomicroscopy examination
- IOP measured using a Goldmann applanation tonometer

Following mydriasis, the following procedures will be performed in the study eye:

- SD-OCT
- Fundus examination
- 3-field fundus photography
- The implant will be viewed to verify its status

If necessary, a second follow-up visit will be scheduled. The format of this follow-up visit should continue until either the subject requires re-treatment (i.e. standard of care rescue treatment), or until 1 month after no residual implant is observed, or to Month 9, whichever comes first, at which point the subject will exit the study.

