A linear model with change from baseline BCVA letters for study eye only as the response, baseline BCVA letters as a covariate, and treatment group as a main effect will be fit to determine treatment group effect with separate models completed for each follow-up visit. These analyses will be used to determine differences in formulations and may be used to assess whether there are differences in outcomes between subjects' data pre- and post-interim to determine whether the data may be pooled. Subjects who receive rescue medication prior to the summarized visit will have their measure replaced with their last observation prior to receiving rescue medication. The least squares mean, standard error, and CI for each treatment group, and the difference between treatment groups will be presented for

study eye only. Additionally, analyses will be completed using individual two-sample t-tests and 90% and 95% CIs around the difference between treatment groups in mean BCVA and mean change from baseline BCVA for study eye only.

Median time (in months) to achieve a treatment response of ≥ 15 letters improvement from baseline in BCVA for study eye and median time (in months) to rescue therapy will be estimated using Kaplan-Meier methods with 90% and 95% CI, calculated using the method of Brookmeyer and Crowley (1982). The log rank statistic will be used to determine differences in time to achieve response between the two treatment groups to determine differences in formulations. Cox proportional hazards will also be used to analyze time to event, including baseline BCVA as a covariate. Results from unscheduled visits or early termination visits will be included in the time to event analysis.

For the event of achieving a treatment response of ≥ 15 letters improvement from baseline in BCVA for study eye, the starting date will be the date of first dose. Subjects receiving rescue medications prior to or on the same date as the achievement of improvement will be considered censored on the day of rescue medication receipt; subjects with neither rescue medications received nor improvement achieved will be considered censored on the last date known to be rescue medication free and improvement achievement free. For the event of receiving rescue therapy, the starting date for the time to event evaluation will be the date of first dose. Subjects who do not receive rescue therapy will be considered censored on the last date known to be event free.

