13.2 SD-OCT, FA and FP

CRT measured by Cirrus (Zeiss) or Spectralis (Heidelberg) instrument will be summarized at each visit, using continuous summary statistics including change from baseline. Comparison between treatment groups for CRT will be performed using the same approaches as specified for BCVA in section 13.1.

Two time to event analyses for CRT of study eye as specified below will be evaluated using the same statistical method for the event of achieving a treatment response of ≥ 15 letters improvement from baseline in BCVA in section 12.1. The starting date of the evaluation will be the date of first dose. Results from unscheduled visits or early termination visits will be included in the time to event analysis.

- Time to resolution of macular edema: defined as first time point at which CRT is less than or equal to 315 μm for study eye.
- Time to loss of resolution of macular edema among treatment responders (population for this analysis includes subjects who achieved resolution of macular edema except on the last day of measurement): defined as first time point at which CRT returns to greater than 315 μm from first achieving the resolution of macular edema.

For the event of resolution of macular edema, subjects receiving rescue medication prior to or on the same date as the achievement of resolution of macular edema will be censored on the day of their rescue medication receipt. Subjects with neither rescue medications received, nor resolution of macular edema will be considered censored on the last date known to be rescue medication free and resolution of macular edema free. For the event of loss of resolution of macular edema after resolution achieved, subjects receiving rescue medications prior to the loss of resolution of macular edema will be considered censored on the day of rescue medication receipt and subjects receiving rescue medications on the same date as loss of macular edema will be considered for loss of macular edema. Subjects with neither loss of resolution of macular edema nor rescue medication received will be considered censored on the last date known to be loss of resolution of macular edema free and rescue medication free.

Total area of capillary non perfusion within ETDRS Grid (16DA) and total area of fluorescein leakage within the ETDRS grid assessed by FA using both Optos instruments (i.e ultra-widfield) and non-Optos (i.e widefield) will be summarized using continuous summary statistics.

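### SAP Section 12 treats implants still visible when observation ends as if their duration were complete, so the visibility summary is a lower bound and should be censored or labelled

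*SAP*

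**What the plan says.** SAP Section 12 defines the duration of implant visibility in days as (end date − injection date) + 1, "where the end date is defined as the latest date at which the implant is visible or date of implant injection" for eyes in which no implant is seen at any follow-up visit. The same formula applies to every eye. The section names no statistic for this variable. The general convention in SAP Section 8.4 would apply: "Summaries for continuous and ordinal variables will include the number of observations (n), arithmetic mean, standard deviation (SD), median, minimum, and maximum". Two companion outputs are planned, a by-visit table ("Vitreous implant visualization will also be summarized at each visit by treatment group using categorical statistics") and a subject listing.

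On the observation schedule, the Protocol synopsis (Study Duration) states: "Residual implant assessment will be performed at Day 8 and at Months 1, 2, 3, 4, 5, and 6", with monthly visits afterwards if needed. Under Protocol Section 7.4, follow-up of a residual implant runs until retreatment, "or until 1 month after no residual implant is observed, or to Month 9, whichever comes first, at which point the subject will exit". Protocol Section 6.10.2 adds: "Any subject may decide to voluntarily withdraw from the study at any time without prejudice".

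The SAP's other time variables do have censoring rules. For time to rescue, Section 13.1 says: "Subjects who do not receive rescue therapy will be considered censored on the last date known to be event free". For loss of macular edema resolution, Section 13.2 says that subjects with neither event "will be considered censored on the last date known to be loss of resolution of macular edema free and rescue medication free".

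**The concern.** An implant still visible at the last assessment has a duration that is known only to exceed the observed value. Section 12 enters it as though it had ended that day. Where the implant was later seen to be gone, it disappeared somewhere between two visits, and the rule takes the earlier one. Both features shorten the reported duration.

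The Protocol sets out to compare two formulations designed to release drug for longer (Sections 1 and 3.2), and it adds visits in Months 7 to 9 because some implants may outlast Month 6. The rule compresses exactly those long durations. CF1 and CF2 values will be read side by side, so a longer-lasting formulation, or unequal early exit, can distort the difference in means. The effect is on description only: no test is planned on this variable, and it is not in the SAP's lists of primary or secondary variables.

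**Working it through.** The plan states no expected duration, proportion visible or exit rate, so there is no plan figure to reproduce.

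**Upper limit.** With months of 30.44 days, the largest value at a nominal Month 9 visit is 9 × 30.44 + 1 ≈ 275 days, or 278 with the +3-day window, however long the implant lasts.

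**Worked arm of 20.** Suppose 7 implants are last seen at Month 5 (153.2 days), 8 at Month 6 (183.6 days) and 5 are still visible at Month 9 (274.9 days).

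- SAP mean: (7 × 153.2 + 8 × 183.6 + 5 × 274.9) / 20 = 195.8 days.
- If those 5 last 1, 2 or 3 months longer, the mean becomes 203.4, 211.0 or 218.6 days. For 2 months the addition is 5 × 60.9 / 20 = 15.2 days.
- If none is visible at Month 9, this part of the error is zero.

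**Simulation.** The inputs are:

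- Visits at days 7, 30, 61, 91, 122, 152, 183, 213, 244 and 274 after injection (from the schedule; the extra initial-phase visit is omitted).
- Weibull disappearance times with shape 3 (assumed).
- 400,000 implants per scenario.
- Early exit of 0% or 20% at Months 4 to 6, independent of visibility (assumed).

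Shortfall = true mean − mean of (last visible day + 1). The part from eyes still visible at last assessment is in brackets.

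| True median (days) | Shortfall, no exit | Shortfall, 20% exit | Eyes of 20 still visible, 0% / 20% exit |
|---|---|---|---|
| 120 | 14 (0) | – | – |
| 150 | 14 (0) | – | – |
| 180 | 16 (3) | 23 (11) | 1.7 / 4.0 |
| 210 | 21 (10) | 31 (22) | 4.3 / 6.5 |
| 240 | 31 (22) | 45 (37) | 7.1 / 9.0 |
| 300 | 65 (60) | 83 (78) | – |

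A dash means the figure is not given here. Varying the shape from 2 to 5 without exit moves the shortfall from 25 to 14 days at a median of 180, from 54 to 18 at 240, and from 96 to 45 at 300.

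**Between formulations** (shape 3, no exit):

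- Medians 150 and 120: a true difference in means of 30 days is reported as 30, because the visit-gap error cancels.
- Medians 240 and 180: 61 is reported as 45.
- Medians 300 and 210: 91 is reported as 46.
- Equal medians of 210 with 0% and 20% exit: reported means of 191 and 181, a 10-day artefact against a standard error of about 20 days at 20 per arm.

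**Median.** Over true medians of 110 to 260 days without exit, the planned median runs from 1 day too long to 30 days too short, depending on where the true value falls between visits. No single figure is typical.

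**The case against.** The best defence is that Section 12 openly defines a last-seen duration and computes it correctly; time to disappearance is a different quantity. Nothing formal depends on it. Durability of effect is covered by time to rescue and time to loss of edema resolution, both censored. Through Month 6 all subjects are scheduled for assessment, so the Month 6 proportion visible is already planned, and the listing shows which implants were still in view.

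The magnitudes can also be challenged. The Protocol supports only a release aim beyond 3 months and partly degraded implants at Week 10 in minipigs. Nothing in it points to medians of 240 to 300 days. At medians of 120 to 180 without exit, censoring contributes 0 to 3 days and the visit gap almost all the rest. The simulated exit at Months 4 to 6 represents withdrawal, not retreatment after Month 6. Moving the 20% exit to Months 7 and 8 gives a censored part of 4 days at 180 and 12 at 210, instead of 11 and 22.

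These points limit the importance of the concern but do not remove it. The variable is titled a duration of visibility and carries no statement that it is a minimum. Table 14.1.5 is given by title only, so its footnotes cannot be checked, but Section 12 asks for none. The by-visit table is not biased by this rule. It is no full substitute either: only eyes with visible implant at Month 6 return for Months 7 to 9, and Section 12 states no denominator for those visits.

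**Conclusion.** The concern holds. Section 12 applies one formula to ended and unended durations, so the reported mean is biased downward even when every implant is seen to disappear, and more so when some are still visible at the end. Under the shape 3 assumption without exit, the shortfall is 14 to 16 days for medians up to 180, nearly all of it visit gap that largely cancels between formulations. It rises to 31 days at 240 and 65 at 300, mostly from censoring, and there it shrinks true differences between formulations. All shapes, medians and exit rates are assumptions, and visibility grading is taken as accurate. Because the item is descriptive and untested, this is a change worth considering, not a threat to the trial's main conclusions.

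**What to change.** **Preferred.** In SAP Section 12, analyse time to non-visibility as interval-censored between the last visible and the first later non-visible visit, starting from injection if the implant is never seen. Right-censor at the last visible visit when no later non-visible visit exists. Report for each formulation:

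- the estimated curve, and the median with its confidence interval or a statement that it was not reached;
- the estimated proportions still visible at Months 6 and 9;
- the number censored, by reason (Month 9, retreatment, withdrawal).

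State that censoring at retreatment may be informative. If Kaplan-Meier on visit dates is used for consistency with Section 13, state that it can overstate the median by up to one visit interval.

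**Minimum.** Keep the planned duration, label it last observed visibility (lower bound), and footnote the number of implants still visible at last assessment.

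**Cost.** One paragraph and one table, or one label and footnote; no new data. In simulated trials of 20 per arm with 20% exit, the preferred method recovered the true proportions visible: 0.63 at Month 6 and 0.21 at Month 9 for a median of 210, and 0.74 and 0.36 for 240. Its drawback is that the median is not reached in about 11% of such trials at a true median of 240 and 76% at 300. The Month 6 and Month 9 proportions must then carry the comparison.
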